STATISTICAL ANALYSIS PLAN

Understanding Factors in Decision Making for Children With Medical Complexity

NCT number: NCT05913206

Last reviewed: August 29, 2025

PI: [name], MS

General Considerations

This randomized factorial experiment examines the effectiveness of uncertainty communication statements and parent narratives for parents of children with medical complexity (CMC). The experiment was nested within a video vignette of a family's visit to a pediatric orthopaedic surgeon regarding potential surgery treatment of their child's neuromuscular scoliosis (NMS). The trial includes 16 possible scenarios based on 4 factors (ambiguity, complexity, normalizing and explanatory language, and narratives) with 2 levels each (present, absent). Participants underwent stratified randomization by language, site, ethnicity, and race.

Study Objectives and Hypotheses

The main objective of the study is to evaluate the effect of various uncertainty communication statements and narratives on decision readiness and additional cognitive, behavioral, and affective outcomes related to decision quality and risk perception.

We hypothesize that participants who receive uncertainty statements and/or narratives will report higher decision readiness without experiencing detrimental effects of increased worry or decreased hope. We hypothesized that these effects would be summative across factors.

Study Design

All participants were recruited from two sites. Eligible parents were at least 18 years old and had a child 0-21 years of age with medical complexity. Randomization was conducted using REDCap, a HIPAA compliant remote data capture system. Participants were not explicitly informed of their group assignment.

The specific trial arms are:

Control condition: Participants in the control condition received a vignette reflective of a typical orthopaedic surgery clinic visit to discuss neuromuscular scoliosis treatment without the addition of any uncertainty communication statements or exposure to parent narratives.

Ambiguity only: This intervention group received a vignette with ambiguity statements embedded in the video.

Complexity only: This intervention group received a vignette with complexity statements embedded in the video.

Normalizing and explanatory language only: This intervention group received a vignette with normalizing and explanatory language about uncertainty embedded in the video.

Narrative only: This intervention group received the control condition vignette followed by a set of parent narratives to read and/or listen to.

Ambiguity and complexity only: This intervention group received a vignette with ambiguity and complexity statements embedded in the video.

Ambiguity and normalizing and explanatory language only: This intervention group received a vignette with ambiguity statements and normalizing and explanatory language about uncertainty embedded in the video.

Ambiguity and narratives only: This intervention group received a vignette with ambiguity statements embedded in the video followed by a set of parent narratives to read and/or listen to.

Ambiguity, normalizing and explanatory language and narratives only: This intervention group received a vignette with ambiguity statements and normalizing and explanatory language about uncertainty embedded in the video followed by a set of parent narratives to read and/or listen to.

Complexity and normalizing and explanatory language only: This intervention group received a vignette with complexity statements and normalizing and explanatory language about uncertainty embedded in the video.

Complexity and narratives only: This intervention group received a vignette with complexity statements embedded in the video followed by a set of parent narratives to read and/or listen to.

Complexity, normalizing and explanatory language, and narratives only: This intervention group received a vignette with complexity statements and normalizing and explanatory language about uncertainty embedded in the video followed by a set of parent narratives to read and/or listen to.

Normalizing and explanatory language and narratives only: This intervention group received a vignette with normalizing and explanatory language about uncertainty embedded in the video followed by a set of parent narratives to read and/or listen to.

Ambiguity, complexity, and narratives only: This intervention group received a vignette with ambiguity and complexity statements embedded in the video followed by a set of parent narratives to read and/or listen to.

Ambiguity, complexity, and normalizing and explanatory language only: This intervention group received a vignette with ambiguity and complexity statements and normalizing and explanatory language about uncertainty embedded in the video.

All: This intervention group received a vignette with ambiguity and complexity statements and normalizing and explanatory language about uncertainty embedded in the video followed by a set of parent narratives to read and/or listen to.

Primary Outcomes

All study measures were categorized into three conceptual domains: affective, cognitive, and behavioral. The primary outcome is decision readiness, measured by the validated PrepDM scale, which is comprised of 10 items each on a 5-point Likert scale from 1=not at all to 5=a great deal. The final score is calculated by summing all responses and transforming to a scale of 0-100 by subtracting 1 from the summed score and multiplying by 25.

The co-secondary outcomes are decisional conflict, intention for NMS treatment (i.e., treatment selected, degree of decision preference), and decision-related knowledge.

Additional exploratory outcomes will also be measured and analyzed (see Table 1).

Table 1. Study Outcomes, Descriptions, and Survey Measure Time Points

Table 1. Study Outcomes, Descriptions, and Survey Measure Time Points		Measure Timepoints
Measure	Description	Time 1
Primary Outcome		
Preparation for Decision Making ¹	A validated scale which will assess participants' perspectives of the decision aid's usefulness in preparing them to communicate with their clinicians and for Shared Decision Making. These questions are answered on a Likert scale ranging from 1=not at all to 5=a great deal.	X
Secondary Outcomes		
Decision Conflict ²	Sixteen questions measuring: 1) perceptions of uncertainty in choosing options, 2) feelings of having adequate knowledge and clear values, and 3) effective decision making. All items use a 5-point Likert scale ranging from 0=strongly disagree to 4=strongly agree.	
Intention for treatment decision	Two items: 1) which treatment option is selected and 2) degree of preference for a particular treatment option	
Decision-related knowledge	5 items about decision-related knowledge	
Exploratory Outcomes		
Affective		
Trust ³	Dugan Physician Trust scale: 5-items on a 5-point Likert scale (1-Strongly Disagree to 5-Strongly Agree). Summary composite outcome variable (range 5-25) with higher scores indicating more trust.	X

Worry	Single unique survey item about the degree of worry that the patient in the vignette will need surgery on a 5-point Likert scale (1- Not at all to 5- Extremely). Based on NCI HINTS. ⁴	
Behavioral		
Intention for not delaying treatment	For those participants who selected surgery as a treatment preference, the urgency with which they would like to pursue surgery.	X
Cognitive		
Risk perception	2 unique survey items scored individually on a 5-point Likert scale (1-very low to 5-very high). Based on NCI HINTS. ⁴	
Parents' Characteristics and Survey Feedback		
Demographics	Participants indicate their age, gender, race, ethnicity, language preference, relation to patient, rurality, employment status, marital status, education level, and household income. Participants also indicate their child's age, gender, race, and ethnicity.	X
Child medical history	Participants indicate their child's use of subspecialists, technology dependence, neurologic impairment, history of prematurity, history of neuromuscular scoliosis, and history of surgery for neuromuscular scoliosis.	X
Readability assessment of video	3-item Likert-scale assessment of video readability.	X
Intolerance of Uncertainty ⁵	Using the IUS-12 validated survey measure to calculate a summary composite variable and associated subdomains of prospective anxiety and inhibitory anxiety. Additional two unique Likert-based items each scored individually, based on NCI HINTS. ⁴	X
Health Literacy ⁶	Chew Health Literacy Scale: 3-item measure on a Likert scale (0-never to 4-always) with summary composite outcome score. Higher score indicates lower health literacy.	X

Numeracy ⁷	Subjective numeracy scale: 8-item measure on a Likert-based scale with a mean composite outcome. Q7 is reverse-coded.	X
Risk taking behavior scale ⁸	DOSPERT: 8-item Likert-based scale from 1-very unlikely to 5-very likely. Mean composite outcome.	X
Hope ⁹	Herth Hope Index: 12-items on a Likert scale (1-strongly disagree to 4-strongly agree). Summary composite outcome with reverse scaling for items hhi3, hhi6.	X
Preferences and values	6-item ranking question where participants are asked to rank particular values in order of most important to least important	X

Planned Data Analysis as of May 2023

Participants who complete the study will be analyzed in the group to which they were randomized, regardless of fidelity. A two-tailed alpha level of 0.05 will be applied to all statistical tests. For the outcomes, we will use standard psychometric analyses (e.g., Cronbach's alpha) will be used to confirm the internal consistency reliability of self-report measures. For the primary outcome variable PrepDM, we will use a 4-way ANOVA model to describe differences in decision preparedness across each factor (ambiguity, complexity, normalizing and explanatory language, and narratives). We will use post-fit marginal estimation to express effect sizes (adjusted means and adjusted mean differences), which incorporates mean centering to make the main effects interpretable in the presence of factor interactions. Regression models, with main effect and interaction terms, can be fitted that are identical to a 4-way ANOVA model. We will use these to model the secondary outcomes, using binary logistic, ordinal logistic, logistic regression for proportions, and linear regression, depending on the level of measurement of the outcome variable, and add covariates including race and education level to all models. We will select covariates using the 10% rule. If we have sufficient power, we will perform exploratory analyses for populations with and without NMS and by ethnicity and language.

Although multiple outcomes will be considered, we have designated a single primary outcome. We do not plan formal multiple comparison adjustments for secondary and exploratory outcomes. Results for secondary and exploratory outcomes will be interpreted based on the overall pattern of results with the awareness that some nominally significant relationships may be false positive findings in the context of multiple analyses.¹⁰

We also do not plan formal multiple comparison adjustments for the randomized comparison between intervention groups, as these comparisons address distinct hypotheses and are thus appropriate for evaluation on a comparison wise basis.¹⁰

Missing data

We will use careful data collection and data management to minimize missing data. If missing data are present in Aim 1 or Aim 3, we will explore patterns of missingness and then impute missing data. We will use the multivariate imputation via chained equations (MICE) approach on both the outcome and predictor variables to create 40 imputed data sets (Graham, et al. 2007)¹⁴⁸, after which coefficients and standard errors are combined using Rubin's rules (Rubin, 1987).¹⁴⁹

Sample size and power calculation for the primary analysis

In a validation study of PrepDM in orthopedic decision making, the scale had mean \pm SD of 3.7 \pm 1.0 after the decision aid intervention. We will randomize n=91 subjects into each of the 2x2x2x2=16 cells of the 4-way factorial design (each factor at 2 levels), for a total N=728 subjects. This is a sufficient sample size to include 4 main effects, 4 two-way interactions, and 3 3-way interactions, without overfitting the data. This provides 80% power, using a two-sided alpha 0.05 comparison, to detect an adjusted mean difference of 3.7 \pm 1.0 vs. 3.4 \pm 1.0 (0.3 standardized mean difference) between the two levels of the factor. That is smaller than a 0.5-point difference on the scale of each item and has been achieved in previous studies of decision aids in orthopedics.

References

2. O'Connor AM. Validation of a Decisional Conflict Scale. *Medical Decision Making*. 1995/02/01 1995;15(1):25-30. doi:10.1177/0272989X9501500105
4. Institute NC. Health Information National Trends Survey (HINTS). Accessed August 5, 2020, 2020. <https://hints.cancer.gov/default.aspx>

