Children's Hospital of Los Angeles (CHLA) will be participating in study procedures. The CHLA study team has received their own independent IRB approval for all study procedures at their own institution (study number: CHLA-22-00281). For Part 1 of the study, the CHLA team will pass along the contact information of all consented CHLA participants via University of Utah REDCap to the University of Utah team for our team to complete virtual study interviews. For Part 2 of the study, the CHLA team will conduct all study procedures with CHLA participants and pass along the contact information of consented participants for the sole purpose of gift card remuneration. All data collected by CHLA will be done through UofU REDCap. The CHLA research assistant will be given limited data access to the University of Utah REDCap project: they will not be able to view University of Utah participant data and will only have access to a limited number of instruments within REDCap that are specific to the study procedures performed at CHLA. No PHI or data from the University of Utah or Primary Children's Hospital will be disclosed to CHLA. More information can be found in the CHLA IRB approved protocol document that is attached in the "Other" section of this application.

Primary outcome: Decision preparedness as measured by the PrepDM validated survey measure. The 10-item (1 to 5 scale) survey measure results in a composite mean score of all items with higher scores indicated greater patient preparedness to make a decision with their provider.

Secondary outcomes: We will collect measures of participant cognitive, affective, and behavioral responses. Cognitive outcomes include: 1) perceptions of risk (adapted from NCI HINTS), 2) perceptions of uncertainty (adapted from the NCI HINTS), 3) knowledge (newly developed). Affective (aka emotional) outcomes include: 1) worry about NMS-related risk (adapted from NCI HINTS), 2) trust in information (adapted from NCI HINTS), 3) hope (Herth Hope Index), and 4) decisional conflict (Decisional Conflict Scale). Behavioral outcomes include: 1) intention for NMS treatment (newly developed) and 2) intention for not delaying treatment (newly developed).

*Newly developed study measures and materials (vignettes and surveys) have been added in an amendment to the IRB protocol.

*Narrative information sheets used in the factorial experiment have been added in an amendment to the IRB protocol.

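### The SAP's scoring formula for PrepDM, the primary outcome, gives 225 to 1225 instead of the stated 0–100; hypothesis tests are unaffected, but reported means and differences would be on the wrong scale

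*SAP*

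**What the plan says.** The SAP's Primary Outcomes section describes PrepDM as "comprised of 10 items each on a 5-point Likert scale from 1=not at all to 5=a great deal". It then gives the scoring rule in two steps. The aggregation step is "The final score is calculated by summing all responses", and the rescaling step is "transforming to a scale of 0-100 by subtracting 1 from the summed score and multiplying by 25". No step divides by the number of items. Table 1 of the SAP repeats the 1-to-5 item coding.

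The protocol defines the same outcome differently, under Primary outcome: "The 10-item (1 to 5 scale) survey measure results in a composite mean score of all items". That is a 1-to-5 score with no transformation.

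The sample-size text in both documents also works on the 1-to-5 scale. It compares means of 3.7 and 3.4 with an SD of 1.0, and the SAP sets the difference against an item-level benchmark: "That is smaller than a 0.5-point difference on the scale of each item".

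Under Planned Data Analysis, the SAP analyses PrepDM by a 4-way ANOVA and expresses effects as adjusted means and adjusted mean differences. Under Missing data, it plans multiple imputation by chained equations, with 40 data sets, for outcomes as well as predictors.

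**The concern.** The formula and the range in the same sentence cannot both be right. A ten-item sum cannot be brought to 0–100 by subtracting 1 and multiplying by 25; those constants fit a single 1-to-5 score, such as the item mean.

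The wording is not a casual use of 'sum' for 'composite'. The sentence refers to summing twice, and Table 1 keeps the two kinds of composite apart: the trust scale is a summary score with range 5 to 25, while numeracy and risk taking are each scored as a mean.

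At stake is the unit of the trial's single primary result. Effects are to be given as adjusted means and adjusted mean differences, so the scale is part of what is reported. A program written to the letter of the SAP would produce figures that cannot be read against the declared 0–100 range, nor against the 0.3 planning difference without conversion.

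**Working it through.** **Inputs.** Ten items, each 1 to 5 (SAP, Primary Outcomes and Table 1). Written rule: (sum − 1) × 25, stated range 0–100 (SAP, Primary Outcomes). Planning means 3.7 and 3.4, SD 1.0, on the item-mean scale (SAP, Sample size and power calculation; the protocol's sample-size paragraph gives the same values).

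**Step 1: try to reproduce 0–100 from the written rule.** The sum runs from 10 × 1 = 10 to 10 × 5 = 50.

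- Minimum: (10 − 1) × 25 = 225.
- Maximum: (50 − 1) × 25 = 1225.

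The stated range is not reproduced.

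**Step 2: try other readings.**

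| Reading | Minimum | Maximum |
|---|---|---|
| (sum − 1) × 25, as written | 225 | 1225 |
| sum × 25 − 1 | 249 | 1249 |
| (item − 1) × 25, added over the ten items | 0 | 1000 |
| (mean − 1) × 25 | 0 | 100 |
| (sum − 10) × 2.5 | 0 | 100 |

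The last two rows are the same score, since (sum/10 − 1) × 25 = (sum − 10) × 2.5. Of the readings tried, only this score gives 0–100.

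**Step 3: relate the written score to the intended one.** Let m be the mean of ten complete items.

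- Written: W = (10m − 1) × 25 = 250m − 25.
- Intended: S = (m − 1) × 25 = 25m − 25.
- Hence W = 10 × S + 225.

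This is an exact linear map. F statistics, p-values, standardized effects and power are the same for W and S. Differences, SDs and confidence-interval widths are multiplied by 10. Means are multiplied by 10 and also shifted by 225.

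**Step 4: put the planning values through each formula.**

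| Quantity | Item mean (1–5) | Intended (0–100) | As written |
|---|---|---|---|
| Higher mean | 3.7 | (3.7 − 1) × 25 = 67.5 | (37 − 1) × 25 = 900 |
| Lower mean | 3.4 | (3.4 − 1) × 25 = 60.0 | (34 − 1) × 25 = 825 |
| Difference | 0.3 | 7.5 | 75 |
| SD | 1.0 | 25 | 250 |
| Difference / SD | 0.3 | 0.3 | 0.3 |

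**Step 5: check that power does not move.** At the SAP's stated total of 728, each level of a factor has 728 / 2 = 364 parents. Two-sided power at alpha 0.05 is about 0.98 on all three scales. That figure is used here only to show invariance. How it sits with the SAP's stated power and cell sizes is a separate question.

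**The case against.** The best case for leaving this alone has three parts. The slip changes no inference, as step 3 shows. It exposes itself, because the first descriptive table would show scores above 100. And the documents point to the repair: the protocol scores by the mean, the planning figures are means, and (mean − 1) × 25 gives exactly the stated range, so the likely cause is that 'summed' was written where 'mean' was meant.

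All of that stands, and it limits how serious the point is. It does not remove the point. An analyst who noticed the impossible range would have to choose the correction alone, and that choice, on the primary endpoint, would be undocumented.

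Several stronger readings are tempting, and the documents do not support them:

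- *Everything reported would be ten times too large.* This is true of differences, SDs and interval widths only. The means are also shifted: 900 against 67.5 is a factor of 13.3, and 825 against 60.0 is 13.75.
- *A sum treats a skipped item as zero.* Neither document says so. The SAP gives no rule for partly answered questionnaires and plans to impute missing outcomes. It does not say whether items or the total score are imputed, so the effect of a skipped item cannot be worked out from the text.
- *The protocol's 1-to-5 mean and a 0–100 score contradict each other.* A correct 0–100 score is a linear rescaling of the mean. Using both is untidy, not contradictory. The planning effect is also stated as a standardized difference, which does not depend on the scale.

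**Conclusion.** The scoring rule for the single primary outcome is wrong as written, and nothing else in either document corrects it. The formula gives 225 to 1225; the stated 0–100 requires the item mean, or equivalently (sum − 10) × 2.5.

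The consequence is confined to the reporting scale: a planning difference of 75 (SD 250) instead of 7.5 (SD 25), and adjusted means outside 0–100. A reader might infer that the factorial tests or the power of the trial are compromised. They are not, because with complete items the two scores differ only by a fixed factor and a constant.

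This rests on two assumptions: that all ten items are present, observed or imputed, before scoring; and that 0–100 is the range the SAP intends, as it says. With items missing at the time of scoring, a sum and a mean are no longer equivalent, and the documents do not allow that effect to be sized.

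**What to change.** Replace the scoring sentence in the SAP's Primary Outcomes section with: *PrepDM score = (mean of the 10 items − 1) × 25, equivalently (sum of the 10 items − 10) × 2.5; range 0–100; higher = better prepared.*

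Leave missing items to the multiple imputation already planned. Wording based on the mean of the answered items should be avoided here: it would bring in a new missing-data rule, with no minimum number of answers, and go beyond correcting the arithmetic.

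Align the protocol's primary outcome definition with this scale, and note beside the sample-size statement that the 0.3 planning difference equals 0.3 × 25 = 7.5 points, with an SD of 1.0 × 25 = 25.

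The cost is one sentence in the SAP, one in the protocol and a short note. No data, design or sample size changes.

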- 2) During the factorial experiment, participants will watch a video of the clinical vignette. Participants will be randomized to receive one of various versions of the vignette that have different combinations of uncertainty communication and randomized to either receive or not receive the narrative information sheet. The experiment will be delivered through University of Utah Research Electronic Data Capture (REDCap). Each participant will receive one version of the vignette. After reading the vignette and the narrative information sheet (if they are randomized to receive it), participants will be asked to answer survey questions including outcome measures, sociodemographic information about them and their child, and information about their child's past medical history (see below primary and secondary outcomes). No identifying information on the participant or their child will be collected. If participants

enroll in the study and start study procedures in-person but do not complete the study, the study team will make follow-up phone calls with the participants to help them complete the study remotely.

Randomization: 2) For the factorial experiment, we will randomize each participant to receive one of eight possible versions of the clinical vignette or clinical vignette and narrative information sheet. We anticipate possibly having up to eight versions of the vignette and/or vignette + narrative information sheet combination. Thus, $n=63$ parents will be randomized to each version. Randomization will occur through the REDCap randomization function after enrollment in the study. The participant and study team members including the PI will be blinded to which condition the participant was assigned to. While study personnel may be present during the experiment for participants who undergo in person recruitment, they will be there for technical support, the participant will complete the experiment on their own.

Study Procedures at secondary site Children's Hospital of Los Angeles:

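### The exploratory urgency outcome is defined only for parents who chose surgery, a choice made after randomisation, so its factor comparison can mislead if a factor changes that choice

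*SAP*

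**What the plan says.** The Behavioral row of SAP Table 1, under the exploratory outcomes, defines urgency this way: "For those participants who selected surgery as a treatment preference, the urgency with which they would like to pursue surgery".

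The choice that forms this subset is itself an outcome. The SAP's Primary Outcomes section names "intention for NMS treatment (i.e., treatment selected, degree of decision preference") among the co-secondary outcomes, and Table 1 describes the measure as "Two items: 1) which treatment option is selected and 2) degree of preference for a particular treatment option".

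The Protocol (Procedures, Study Procedures, item 2) puts the survey after the randomised material: "After reading the vignette and the narrative information sheet (if they are randomized to receive it), participants will be asked to answer survey questions including" the outcome measures.

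The Protocol's Secondary outcomes paragraph reads: "Behavioral outcomes include: 1) intention for NMS treatment (newly developed) and 2) intention for not delaying treatment (newly developed"). It states no restriction to parents who chose surgery, and it does not say who answers the item. The SAP moves the outcome to the exploratory tier, about which it says "Additional exploratory outcomes will also be measured and analyzed (see Table 1").

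The SAP's Planned Data Analysis section analyses completers in their randomised group, adds covariates including race and education, and cautions about false positives from multiple analyses. Its Missing data section applies MICE to outcomes and predictors. Neither section has a rule for an outcome that exists only in a subset.

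**The concern.** Randomisation makes all parents comparable across the levels of a factor. It does not do so for the parents who go on to choose surgery, if the factor affects who they are. Suppose a factor persuades some hesitant parents to choose surgery. They join the choosers at that level and lower its average urgency, although no parent's urgency has changed. A factor that moves hesitant parents away from surgery does the reverse.

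The trial sets out to look for such movement. The SAP's stated objective covers effects on "decision readiness and additional cognitive, behavioral, and affective outcomes related to decision quality and risk perception", and treatment selected is one of the outcomes tested. Nothing else in the plan deals with the selection:

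- Analysis as randomised does not restore balance inside a subset formed by a later response.
- Race and education are not a model of what drives the choice of surgery.
- The false-positive caution concerns multiplicity.
- The MICE text leaves open whether urgency in a non-chooser is missing or not applicable. Imputing it would create an urgency for surgery that the parent did not select.

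The Protocol says that helpful and effective results will go into a decision support tool. An apparent effect on urgency that only reflects who chose surgery could mislead that step.

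**Working it through.** The documents give no share choosing surgery, effect size, SD or power for urgency, so there is no stated figure to reproduce. The calculation below is an illustration.

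**Inputs from the documents.** Two-sided alpha is 0.05 (SAP, Planned Data Analysis). N=728 is the total stated in the SAP sample-size section, which is 728/2 = 364 per level of a factor. That section's cell size does not match its total (91 × 16 = 1,456), and the Protocol gives 1,008 for the experiment. N affects only the rejection rate, not the artefact.

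**Assumptions.** Each parent has a standard normal latent preference for surgery and chooses surgery when it exceeds a cut-off c. The factor moves only the cut-off. Urgency has SD 1 among all parents and correlation ρ with preference. The factor has no true effect on urgency. The test is a plain comparison of two means, without the other factors or covariates.

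**Formulas.** With share p choosing surgery, c = Φ⁻¹(1 − p) and λ = φ(c)/p. Among choosers, mean urgency is ρλ and its variance is 1 − ρ²λ(λ − c).

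**Worked case: 50% v 60%, ρ = 0.5**

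- p = 0.50: c = 0, λ = 0.798, variance = 1 − 0.25 × 0.798 × 0.798 = 0.841, n = 364 × 0.50 = 182.
- p = 0.60: c = −0.253, λ = 0.644, variance = 1 − 0.25 × 0.644 × 0.897 = 0.856, n = 364 × 0.60 = 218.4.
- Artefact = 0.5 × (0.644 − 0.798) = −0.077 SD.
- Standard error = √(0.841/182 + 0.856/218.4) = 0.092, so |artefact|/SE = 0.83.
- Rejection rate = Φ(0.83 − 1.96) + Φ(−0.83 − 1.96) = 13.3%.

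**Range.** Absolute artefact in SD and rejection rate at N=728, for ρ = 0.3 / 0.5 / 0.7:

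| Choosing surgery | Artefact (SD) | Rejection rate (%) |
|---|---|---|
| 50% v 50% | 0 / 0 / 0 | 5.0 / 5.0 / 5.0 |
| 50% v 55% | 0.023 / 0.039 / 0.055 | 5.6 / 7.0 / 9.8 |
| 50% v 60% | 0.046 / 0.077 / 0.108 | 7.6 / 13.3 / 25.0 |
| 50% v 70% | 0.090 / 0.151 / 0.211 | 16.0 / 38.9 / 72.9 |
| 30% v 40% | 0.058 / 0.097 / 0.135 | 7.6 / 13.4 / 26.3 |
| 70% v 80% | 0.044 / 0.073 / 0.103 | 8.2 / 14.9 / 27.6 |

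At ρ = 0 the artefact is zero for any shares. At the upper limit, ρ = 1, the 50% v 60% artefact is 0.798 − 0.644 = 0.154 SD. At N=1,008, the 50% v 60% rejection rates are 8.6%, 16.5% and 32.6%.

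**Simulation check.** At ρ = 0.5 and N=728, 4,000 simulated trials per case rejected 5.1%, 12.7% and 38.9% of the time for 50% v 50%, 60% and 70%.

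**Hidden effect.** At ρ = 0.5, a true +0.15 SD effect on urgency would appear as 0.15 − 0.077 = +0.073 SD with 50% v 60%. With 50% v 70% it would appear as 0.15 − 0.151, about zero.

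**The case against.** The best defence is that urgency of pursuing surgery has no natural value for a parent who did not select it, so asking only choosers is sensible. Those parents still count in treatment selected and in degree of preference. Both rank higher than urgency and carry no stated restriction, so a shift in choice would be visible. Urgency is one exploratory row in Table 1, and the SAP says it will read such results on the overall pattern. An all-parent composite also answers a different question and partly repeats the treatment-selected analysis.

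Much of this stands. It keeps the severity low and is a fair cost of the remedy. It does not remove the problem, because the SAP never ties the reading of urgency to the share choosing surgery.

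Three stronger readings are tempting, and the documents do not support them:

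- A reader might infer that the factors are expected to change treatment choice. The SAP hypothesis concerns decision readiness, worry and hope. Listing treatment selected as an outcome means only that a shift will be tested.
- A reader might infer that the Protocol requires urgency from every participant and that the SAP contradicts it. The Protocol names the outcome and is silent on who answers.
- A reader might infer that a known, large part of the sample is discarded. The share not choosing surgery is not given.

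**Conclusion.** The point holds in conditional form. The choosers-only comparison is not protected by randomisation if a factor changes the choice of surgery and urgency is related to what drives that choice. If either condition fails, this selection mechanism causes no bias. A flat statement that the urgency effect is biased would therefore go too far.

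On the assumed shares and correlations, the artefact runs from nothing to about 0.2 SD. For a 10-point shift from 50% to 60% it is about 0.05 to 0.11 SD, with rejection rates of about 8% to 25% in place of 5%. The figure of 0.15 SD for that shift needs urgency and preference to be the same quantity, so it is a limit and not a typical value.

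Severity is low. The outcome is exploratory, and neither the primary PrepDM analysis nor the secondary outcomes are affected.

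**What to change.** Amend the SAP in four places:

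1. For any factor comparison, define one ordered variable in all randomised participants, with surgery not selected as the lowest category and then surgery selected by increasing urgency. Analyse it by ordinal logistic regression, which the SAP already names for secondary outcomes, and check proportional odds.
2. Report the share choosing surgery at each factor level beside it.
3. Label urgency among choosers as descriptive only.
4. State that urgency of parents who did not choose surgery is not applicable and is not imputed by MICE.

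The cost is SAP wording and a recode of two items already planned for collection. The recode assumes that the urgency responses are ordered, since their format is not given. The new variable measures willingness for timely surgery and not urgency alone. It overlaps with treatment selected, and a single odds ratio cannot separate an effect on choice from an effect on urgency. The SAP describes randomisation in the past tense, so the change should be dated and made before any unblinded analysis, or else labelled post hoc.
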